**B. Specific Aims:** Anticoagulation is routinely administered prior to performing PCI in interventional cardiology practice and intensity of anticoagulation is monitored using POC testing for the ACT. However, current target values were derived from older, case-control studies (6,16), and supported by post-hoc retrospective analysis from trials of antithrombotic therapies (9,10). In the modern era of high rates of dual antiplatelet therapy use, low profile devices, greater attention to access site management, and shorter procedural duration, the optimal ACT target for PCI remains unknown. The overall objective of this proposal is to identify the optimal range of the activated clotting time (ACT) during percutaneous coronary intervention (PCI) that is associated with the lowest rates of adverse clinical events. The optimal ACT target during PCI has not previously been investigated in a prospective clinical trial, leaving uncertainty regarding the level of anticoagulation intensity during coronary revascularization procedures. We hypothesize that in the modern cardiac catheterization laboratory, where PCI procedural duration is relatively short and rates of intracoronary stenting and dual antiplatelet therapy use is high, lower ACT targets, as compared with higher ACT targets, will be associated with lower rates of bleeding while having similar rates of ischemic events. The specific aims of this study are as follows:

**B.1.1 Aim 1 (Primary):** The primary aim of this study of patients undergoing PCI is to compare the risk of bleeding in patients randomized to a low ACT target to those randomized to either a medium or high ACT target. We hypothesize that the risk of bleeding will be lower in those with a low ACT target compared to those with a medium ACT target as well as those with a high ACT target. See Figure 1 for ACT target ranges.

**B.1.2 Aim 2 (Primary):** We aim to estimate the incidence of both our primary study outcome (bleeding) and our primary safety endpoint (NACE) separately for those with a low, medium, and high ACT target.

**B.1.3 Aim 3 (Primary):** We aim to establish whether there is evidence of non-inferiority of a low ACT target compared to a high ACT target with respect to the proportion of patients undergoing

PCI with respect to NACE. We hypothesize that the rate of NACE is the same as or lower than that for patients with a high ACT target.

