#### F. Statistical Considerations:

**F1. Randomization and blinding:** Patients will be randomized (1:1:1) to one of the three ACT target groups (low, medium, or high) using a dynamic minimization algorithm so as to optimize the likelihood that balance between the low, medium, and high ACT target groups will be

achieved with respect to sex (male or female) and glomerular filtration rate (30 to 59 ml/min/1.73m^2 or ≥60 ml/min/1.73m^2). The algorithm will be implemented in RAVE RTSM, a secure web-based interface, and accessed by the study coordinator or other appointed study personnel. Randomization will be conducted after the diagnostic portion of the procedure on only patients who will require ACT monitoring. Since eligible patients will require ACT monitoring during PCI, we will not conduct the study in a strictly blinded fashion. However, study participants will not be informed of their randomization assignment.

**F2. Data collection and handling:** Electronic case report forms along with a corresponding secure REDCap database will be created for data collection (29). Data to be collected will include baseline demographics, comorbidities, procedural variables, in-hospital events, NACE component, and adverse events.

**F3: Definition of study outcomes:** Study endpoints are summarized in Appendix II.

**F3.1 Primary study endpoint:** Our **primary study endpoint is bleeding** and is defined as either a Bleeding Academic Research Consortium (BARC) hemorrhage grade of 1, 2, 3, or 5 or an EASY hematoma scale grade of I-V from the time of PCI to the time the patient is discharged from the hospital.

**F3.2 Primary safety endpoint:** Our **primary safety endpoint is a composite of net adverse clinical events (NACE) and stent thrombosis**, as defined by the Academic Research Consortium, from the time of PCI to the time the patient is discharged from the hospital.

**F3.2.1 NACE** is the composite of all-cause mortality, myocardial infarction (MI), stroke, target lesion revascularization, and major bleeding within 30 days after PCI.

**F3.2.2 MI** will be defined as any two of the following 3 criteria: 1) chest pain for at least 20 minutes; 2) elevation of cardiac biomarkers, preferably troponin, above the laboratory upper limit of normal; and 3) new pathological Q wave on electrocardiogram.

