two-sided overall 5% significance level with Bonferroni adjustment for multiple testing ( $p$  value  $\leq 0.025$  considered as statistically significant) to detect an absolute difference in in-hospital bleeding (Aim 1) between the low ACT target and the medium ACT target (ie. 5% vs. 15%) in addition to a 20% absolute difference between the low ACT target and the high ACT target (ie. 5% vs. 25%). The power was estimated on the basis of 5000 simulations. Patients meeting eligibility criteria for the study and who consent for participation but that do not undergo randomization due to either not receiving intracoronary diagnostic imaging (IVUS/OCT) or physiologic testing (iFR/FFR) or PCI will be entered into the ACT registry and observed for clinical events, including 30-day outcomes. The reason these patients are not categorized as screen failures is because the final criterion for eligibility is receipt of PCI, a criterion that is not known until the coronary angiogram is performed which is after patients have signed informed consent. Because patients receive moderate sedation during their procedure as part of standard of care, ethical and scientific prudence dictates that informed consent be obtained prior to procedural start. True screen failures, therefore, are those subjects not meeting study inclusion or exclusion criteria. . Based on current lab practice patterns at our institution, it is anticipated that approximately 20% of patients who enroll in the study will not require ACT monitoring after the diagnostic portion of the procedure, therefore we intend to consent up to 780 patients. In 2016, there were 240 PCI procedures and 220 adjunctive coronary imaging/physiology procedures (Fractional Flow Reserve = 158, Intravascular Ultrasound = 59, Optical Coherence Tomography = 12) establishing the feasibility of performing the study and meeting patient accrual targets over an **18 - 24 month period.**

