## F5. Statistical analysis plans:

F5.1 Patient population for analysis: The primary analysis will include all randomized patients. Since patients will be randomized after the diagnostic portion of the procedure and the primary study outcome will be collected during their initial hospitalization after PCI, we anticipate negligible loss to follow-up and negligible imbalance between study arms. Analysis of the study aims will be conducted using an intent-to-treat approach, which means it will be an analysis including all randomized patients according to the group they were randomized regardless of whether or not the assigned ACT target was achieved.

F5.2 Primary analysis plan: Aim 1: The risk of in-hospital bleeding in the medium ACT target group and the high ACT target group will be compared to the risk of in-hospital bleeding in the low ACT target group using pair-wise chi-square tests (or Fisher's exact test). Relative risks and 95% confidence intervals will be reported. For these two tests of the primary study outcome, a two-sided p-value  $\leq 0.025$  will be considered statistically significant using the Bonferroni adjustment for multiple testing. This means that the overall two-sided level of significance for the trial will be 0.05. Aim 2: We will estimate the proportion of patients with each outcome (bleeding, NACE) along with 95% confidence intervals for the proportions using the Wilson score method separately for the three groups. Aim 3: We will create a 95% confidence interval for the difference in proportions of patients with NACE in the low and high ACT target groups using the Newcombe score method. This will be used to assess whether there is evidence of non-inferiority of low ACT target compared to high ACT target according to the definition in section F3.4.

F5.3 Secondary analysis plan: We will evaluate if associations between ACT target group (low, medium, high) and in-hospital bleeding are independent of sex, access site, and concomitant use of glycoprotein (GP) IIb/IIIa inhibitors (Aim 2) using a Cochran-Mantel-Haenszel test. For these pre-planned tests, a two-sided p-value  $\leq 0.0167$  will be considered statistically significant using a Bonferroni adjustment for multiple testing. Descriptive summaries and relative risks will be reported as in the primary analysis, except stratified by each of the patient or procedure characteristics.

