Baseline patient and procedure characteristics of the three groups will be reported as number and percentage for categorical variables and median and interquartile range for continuous variables. To evaluate the possibility of imbalance, we will make comparisons between the three randomized groups using a Kruskal-Wallis test for ordered or numeric variables and a chi-square test (or Fisher's exact test) for categorical variables. For those baseline characteristics with imbalance between groups, we will summarize the number and percentage as well as relative risk and 95% confidence intervals as was done with the pre-planned analyses of sex, access site, and concomitant use of glycoprotein (GP) IIb/IIIa inhibitors with stratification by the baseline characteristic. In addition, we will use a multivariable logistic regression model with in-hospital bleeding as our outcome measure and fixed effects for group (reference group = low ACT target), sex, access site, concomitant use of glycoprotein (GP) IIb/IIIa inhibitors, and any other baseline characteristics with evidence of potential imbalance between groups (p-value  $\leq 0.20$ ) allowing no more than one variable for every 10 patients who experience in-hospital bleeding.

F5.4 Exploratory analysis plan: We will explore the association of ACT target with individual components of bleeding and NACE using a Cochran-Armitage trend test and report the number and percent of patients with each component separately for each group. Adjustment for multiple testing will be conducted using the Holm step-down method.

F5.5 Interim analysis plan: A blinded review of the study's overall incidence of the primary study outcome and the primary safety endpoint will be planned after 50% of patients have completed the study. If this review suggests that assumed incidence used to plan the study is much higher than the actual event rate then we may reestimate the sample size to ensure the study is adequately powered. Since the analysis will be conducted blind to group assignment this will not introduce statistical bias and adjustment to the study's significance level is not required...

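### Improvement, not an error: Holm in place of Bonferroni for the two Aim 1 bleeding tests would raise low-versus-medium power from 81.1% to 88.5% with the same 504 patients

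*Combined protocol and SAP*

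**What the plan says.** B.1.1 (Aim 1) hypothesises that bleeding under the low target is lower "compared to those with a medium ACT target as well as those with a high ACT target", so both comparisons matter. F4 sizes the trial at 504 patients for more than 80% power at a "two-sided overall 5% significance level with Bonferroni adjustment for multiple testing". The planning rates are 5% versus 15% (low versus medium) and 5% versus 25% (low versus high).

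F5.2 makes the two comparisons "using pair-wise chi-square tests (or Fisher's exact test", without saying when each test applies. Each p-value of 0.025 or less "will be considered statistically significant using the Bonferroni adjustment for multiple testing". For the effect sizes, "Relative risks and 95% confidence intervals will be reported", with no mention of a multiplicity adjustment for the intervals. For the exploratory component analyses, F5.4 chooses differently: "Adjustment for multiple testing will be conducted using the Holm step-down method".

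On the smaller point, F1 minimises allocation so that balance is "achieved with respect to sex (male or female) and glomerular filtration rate". The Aim 1 tests use neither factor. Sex appears in the F5.3 Cochran-Mantel-Haenszel test and as a fixed term in the logistic model. GFR group has no fixed place in any analysis; it can enter only among "any other baseline characteristics with evidence of potential imbalance between groups", at p ≤ 0.20.

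**The concern.** Single-step Bonferroni holds the second comparison to 0.025 even after the first has been rejected. Familywise control does not require this: once one null hypothesis is rejected, only one remains that could be falsely rejected, and it can be tested at the full 0.05. Holm's rule uses this and keeps every rejection that Bonferroni makes. The plan therefore applies the less powerful procedure to its primary tests and the more powerful one to its exploratory tests.

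Low versus high is almost certain to succeed at the planning rates, so nearly all the risk to Aim 1 lies in low versus medium. That comparison clears the promised 80% by only about one point.

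**Working it through.** **Inputs.** 504 patients allocated 1:1:1, so 168 per arm (F4); bleeding rates 5%, 15% and 25% (F4); overall two-sided level 0.05 and 0.025 per test (F4, F5.2); negligible loss to follow-up (F5.1).

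**The plan's own figure.** Normal approximation for low versus medium at 0.025, with average rate 0.10:
- pooled SE = √(2 × 0.10 × 0.90 / 168) = 0.03273
- unpooled SE = √((0.05 × 0.95 + 0.15 × 0.85) / 168) = 0.03228
- power = Φ[(0.10 − 2.2414 × 0.03273) / 0.03228] = Φ(0.825) = 79.5%

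Exact enumeration of the three binomial counts, keeping the shared low arm, gives 81.15% for low versus medium, 99.94% for low versus high and 81.14% for both (uncorrected chi-square). The statement in F4 is reproduced. With Fisher's test the low-versus-medium figure is 76.4%.

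**Holm.** Low versus medium is rejected if p_M ≤ 0.025, or if p_M ≤ 0.05 and p_H ≤ 0.025. For each low-arm count x, let r₂₅(x) and r₅(x) be the probabilities that p_M is at most 0.025 and at most 0.05, and h₂₅(x) the probability that p_H ≤ 0.025. Then

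power = Σₓ P(x) · [r₂₅(x) + (r₅(x) − r₂₅(x)) · h₂₅(x)].

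| Rates low/medium/high | Test | Low vs medium, Bonferroni | Low vs medium, Holm |
|---|---|---|---|
| 5/15/25% (planned) | chi-square | 81.1% | 88.5% |
| 5/15/25% (planned) | Fisher | 76.4% | 83.8% |
| 5/15/15% | chi-square | 81.1% | 86.1% |
| 5/15/15% | Fisher | 76.4% | 81.1% |
| 10/20/30% | chi-square | 63.9% | 73.7% |
| 5/12/18% | chi-square | 53% | 64% |
| 5/10/25% | chi-square | 30.1% | 41.4% |
| 5/15/10% | chi-square | 81.15% | 81.99% |

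Both comparisons significant (chi-square): 81.1% to 88.5% at 5/15/25%, and 70% to 80% at 5/15/15%.

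**In patients.** Under Bonferroni, 88.5% power (chi-square) needs about 201 per arm: 3 × 201 = 603, and 603 − 504 = 99 more. With Fisher's test, Bonferroni needs about 180 per arm (540) to reach 80%.

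**Error rates.** With all three rates equal (5% to 25%), the chance of any false rejection is 4.0–4.7% (chi-square) or 2.3–3.4% (Fisher), the same under either rule. With low equal to medium and high different, the chance of falsely rejecting low versus medium is:

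| Rates | Chi-square, Bonferroni to Holm | Fisher, Bonferroni to Holm |
|---|---|---|
| 5/5/25% | 2.2% to 4.9% | 1.2% to 2.6% |
| 10/10/30% | 2.4% to 5.1% | 1.6% to 3.1% |
| 15/15/35% | 2.5% to 4.9% | 1.7% to 3.4% |

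**Minimisation factors.** The documents give neither the prevalence of a factor nor its strength for bleeding. Assume one perfectly balanced factor with prevalence 20–50%, and simulate 400,000 trials per setting. Stratifying then adds about 0.1 points of power at an odds ratio of 1.5, 0.3 at 2, 0.8–1.0 at 3 and 1.6–2.3 at 5.7. The size of the unadjusted test is 2.5%, 2.4%, 2.3% and 1.9–2.1% against a nominal 2.5%. Ignoring the factor is slightly conservative; it does not inflate error.

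**The case against.** - **Nothing is broken.** Bonferroni is valid and F4's power is met with chi-square. This stands, and the point is offered as an improvement.
- **The Fisher figures may never apply.** If Fisher's test is only a fallback for sparse tables, it would practically never be used at the planning rates: the expected number of events per arm is (8.4 + 25.2) / 2 = 16.8. On that reading 76.4% is not the plan's power. But F5.2 states no such rule, and the chi-square gain does not depend on it.
- **Holm has a cost.** False rejection of low versus medium about doubles when low and medium are equal and high differs. True, but it rises only to about the level the trial has accepted overall. The 5.1% at 10/10/30% comes from the chi-square approximation, which also puts Bonferroni at 2.53% against 2.5% at 15/15/35%.
- **The gain leans on a strong high-arm effect.** It does: 5.0 points at 5/15/15% and 0.8 at 5/15/10%. It shrinks but cannot become a loss.
- **A late change can look opportunistic.** Only participants are kept unaware of allocation (F1), and the documents do not give enrolment status. The change should therefore be dated and made before outcomes by arm are seen.
- **The GFR point is separate and minor.** Agreed; nothing above depends on it.

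**Conclusion.** The point holds. At F4's planning rates with 168 per arm, Holm adds 7.4 points of power on the comparison that decides Aim 1 (81.1% to 88.5%, chi-square; 76.4% to 83.8%, Fisher). It keeps the same nominal 5% familywise level and needs no more patients. The size of the gain rests on low versus high usually being significant at 0.025. Holm does not rescue a small low-versus-medium difference: at 5/10/25% power is still only 41.4%. The familywise level here covers the two Aim 1 tests; the Aim 3 non-inferiority assessment lies outside it under either rule. The change is worth making, but the current rule is not a defect. The omission of GFR group is a small matter, worth about 0.1–0.3 points of power at assumed odds ratios of 1.5–2.

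**What to change.** Before any unblinded data are seen, reword the decision rule in F5.2 and the matching sentence in F4: *The smaller of the two Aim 1 p-values is tested at 0.025; if it is significant, the other is tested at 0.05 (Holm), for an overall two-sided level of 0.05.* In the same edit, state whether chi-square or Fisher's test is used, because that decides whether the present plan reaches 80%.

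The sample size stays at 504 and no new data are needed. Holm has no simple matching simultaneous intervals, but the planned 95% intervals for the relative risks are unadjusted already, so none is lost. The statistical price is the higher, still about nominal, false-rejection chance shown above.

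As a minor addition, make GFR group (30–59 versus ≥60) a fixed covariate in the F5.3 logistic model; it is already recorded for randomisation. Optionally, stratify the Aim 1 comparisons by sex and GFR group (Mantel-Haenszel) and keep the unadjusted chi-square as a sensitivity analysis.

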B.1.4 Aim 4 (Secondary): We aim to study the impact of sex, access-site (i.e., radial vs femoral), and concomitant use of glycoprotein (GP) IIb/IIIa inhibitors on the association of ACT target with bleeding. It has been shown that female sex is associated with higher ACT targets during PCI (17), and work from our group has shown an important observed interaction with myocardial infarction risk in women, but not men, with ACT targets >350 seconds(18). This observation of a potential differential sex-specific interaction has not previously been reported and requires validation in a prospective study. In addition, it has previously been shown that women appear to be at higher risk for developing forearm bleeding complications after transradial catheterization. The use of transradial PCI has steadily increased in the United States, though adoption of this technique remains lower than that observed in Canada and Europe. However, recent internal PCI data from the cardiac catheterization laboratory at Mayo Clinic Rochester has shown increasing utilization of the radial artery for PCI, now over 50%. At Mayo Clinic Florida, the percentage of radial access is over 70% and is considered the default access site for catheterization. It remains unknown whether ACT targets can be similarly interpreted for radial PCI, as these original targets were derived from studies in primarily transfemoral access cohorts with larger vascular access sheaths. Finally, the additional use of GP IIb/IIIa inhibitors in UFH-treated patients has been associated with higher rates of major and minor bleeding (9), thus lower ACT target values (i.e., 200-250 sec) are recommended in patients concomitantly treated with these agents. In the Mayo Clinic experience, there was no apparent interaction by GP IIb/IIIa inhibitor status when testing the association of ACT values to outcomes, however, baseline characteristics of groups receiving or not receiving these agents differed and residual confounding may have been present (18). The OPTIMAL-ACT trial will incorporate a pre-specified analysis with specific ACT targets in patients receiving GP IIb/IIIa inhibitors to better understand ACT targets and outcomes.

B.1.5 Aim 5 (Exploratory): We will explore the association of ACT targets with individual components of NACE and stent thrombosis for purposes of hypothesis generation.

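### Aim 4 asks whether sex, access site and GP IIb/IIIa use change the ACT-bleeding association, but the only test F5.3 assigns to these factors is a Cochran-Mantel-Haenszel test, which does not compare strata

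*Combined protocol and SAP*

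**What the plan says.** Section B.1.4 sets the question: "We aim to study the impact of sex, access-site (i.e., radial vs femoral), and concomitant use of glycoprotein (GP) IIb/IIIa inhibitors on the association". The association meant is the one between the ACT target and bleeding. The section describes the institution's earlier GP IIb/IIIa result in the same terms: "there was no apparent interaction by GP IIb/IIIa inhibitor status when testing the association of ACT values to outcomes".

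F5.3 gives the analysis: "We will evaluate if associations between ACT target group (low, medium, high) and in-hospital bleeding are independent of sex, access site, and concomitant use". The third factor is use of GP IIb/IIIa drugs. The same sentence goes on to name the aim and the method: "inhibitors (Aim 2) using a Cochran-Mantel-Haenszel test". Each of the three tests is judged at a two-sided 0.0167. F5.3 adds: "Descriptive summaries and relative risks will be reported as in the primary analysis, except stratified by each of the patient or procedure characteristics". The primary analysis in F5.2 says "Relative risks and 95% confidence intervals will be reported", so the stratified estimates should carry intervals too.

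F5.3 then describes a multivariable logistic model for bleeding with fixed effects for group, the three factors and any imbalanced baseline variables, limited to one variable per 10 patients who bleed. It contains no product term. Neither an interaction test nor a homogeneity test is named anywhere in the plan.

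**The concern.** The aim and its test address different hypotheses. The CMH null is that ACT group and bleeding are unrelated within every stratum. Rejecting it shows an association after stratification. It does not show whether that association is the same in women and men, or with radial and femoral access.

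The 0.0167 threshold is attached to CMH, so its p-value is the natural candidate for the reported Aim 4 result. A significant value could be taken as evidence that a factor matters, or that the effect holds in every stratum. A non-significant one could be taken as no modification. None of these conclusions would follow. The label Aim 2 in F5.3 adds to the confusion, because Aim 2 in B.1.2 is the estimation of incidence.

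**Working it through.** **Plan figures first.** Three tests: 0.05/3 = 0.0167, as stated. Arm size: 504/3 = 168. Planning rates for low/medium/high ACT target are 5/15/25% (F.4).

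**The two tests.** Let stratum k have N_k patients and m_k bleeds, and let group g in that stratum have n_kg patients and x_kg bleeds.
- CMH: d_g = Σ_k (x_kg − m_k·n_kg/N_k); Q = d′V⁻¹d on 2 df. The deviations are summed over strata before testing, so differences between strata are not examined.
- Interaction: logit(p_kg) = a + group_g + stratum_k + (group×stratum)_gk. The likelihood-ratio test that the product terms are zero has 2 df.
- Critical value for both: −2·ln(0.05/3) = 8.19.

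**Assumptions.** B.1.4 says of the Florida laboratory that "the percentage of radial access is over 70% and is considered the default access site for catheterization", so 30% is used for the smaller stratum. The documents give no trial-specific shares and no stratum-specific rates. The larger stratum has 5/15/25%; the smaller-stratum rates below are illustrative. The rates were simulated with at least 20,000 trials per scenario.

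The pooled rate is 0.7 × larger-stratum rate + 0.3 × smaller-stratum rate. For no gradient: low 0.7×5 + 0.3×15 = 8%; medium 15%; high 0.7×25 + 0.3×15 = 22%.

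| Smaller stratum | Pooled low/medium/high | High minus low | CMH rejects | Interaction test rejects |
|---|---|---|---|---|
| 5/25/45% (steeper) | 5/18/31% | 26 points | 100% | 8% |
| 5/15/25% (no modification) | 5/15/25% | 20 points | 99.7% | 2% |
| 10/15/20% (half gradient) | 6.5/15/23.5% | 17 points | 96% | 11% |
| 15/15/15% (no gradient) | 8/15/22% | 14 points | about 82–83% | 46% |
| 25/15/5% (reversal, extreme) | 11/15/19% | 8 points | 27% | 99% |

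The CMH column follows the pooled spread, not the difference between strata. With 10/12/14% in both strata (spread 4 points) CMH rejects in 7%. With reversal in two equal strata (pooled 15/15/15%) it rejects in about 1.5%, near its nominal level, although modification is then at its strongest.

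**Power of the interaction test** at smaller-stratum shares of 10/20/30/40/50%:
- no gradient: 21/35/46/52/54%
- half gradient: 7/9/11/13/13%

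**Sparse cells.** At a 30% share the low-arm cell expects 168×0.30×0.05 = 2.5 bleeds. The documents give no GP IIb/IIIa share; at an assumed 2% or 5% that cell expects 168×0.02×0.05 = 0.17 or 168×0.05×0.05 = 0.42 bleeds.

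**Covariate cap.** Expected bleeds: 168×(0.05+0.15+0.25) = 75.6, which allows 7 variables. Counted in degrees of freedom, group (2) plus three factors (3) plus one interaction (2) already makes 7. Adding the interaction to the planned model would leave no room for imbalanced covariates.

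**The case against.** The best defence is that F5.3 can be read as asking whether the ACT effect persists after adjustment for each factor. CMH is a coherent test of that, and nothing in the plan says its p-value will be read as effect modification. This stands as far as it goes, but it leaves Aim 4 without any test. The matching list of three factors makes Aim 4 the evident target.

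It is also fair that stratum-specific relative risks with intervals are already planned, and that an interaction test would be weak. Both points limit the gain from the change. They do not justify testing a different hypothesis.

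Some stronger readings are tempting but unsupported:
- A reader might infer that CMH is the only formal test in F5.3. It is not: F5.3 also has baseline-imbalance tests and the logistic model. CMH is the only test assigned to the three Aim 4 factors.
- A reader might infer that the plan ignores differences between strata. It reports estimates by stratum, but without a formal comparison.
- A reader might infer that the plan sets out to confirm a known sex interaction for bleeding. The sex interaction cited in B.1.4 concerned myocardial infarction.
- A reader might infer that the primary comparison is compromised. It does not use this test.

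**Conclusion.** The mismatch is real and should be corrected. As written, the test for Aim 4 cannot separate a uniform ACT effect from one that varies: CMH rejects in about 99.7% of trials when the factor changes nothing and still in about 82% when the smaller stratum has no gradient, against about 2% and 46% for a test aimed at the question. That CMH does not compare strata follows from its definition and needs no assumption. The percentages rest on the planning rates, an assumed 30% smaller stratum and illustrative stratum rates; other shares and rates would change them. The consequence is confined to a secondary aim.

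**What to change.** 1. For sex and access site, make the Aim 4 test an ACT group × factor interaction (or homogeneity) test at the existing 0.0167. Fit a separate logistic model per factor with only group, factor and their product, so that the covariate cap on the multivariable model is untouched.
2. Pre-specify an exact or penalized-likelihood version and the sparse-cell condition that triggers it.
3. State that the test is on the odds-ratio scale. Rates of 5/15/25% and 10/30/50% have the same high-versus-low relative risk (5), but odds ratios of (0.25/0.75)/(0.05/0.95) = 6.3 and (0.50/0.50)/(0.10/0.90) = 9.0. Report the test beside the planned stratum-specific relative risks and intervals.
4. Add a caveat for access site. The Rationale and Appendix II tie the EASY scale to transradial (or ulnar) access, so a radial-femoral interaction may partly reflect how the outcome is defined. Reconcile whether BARC 1 counts: F3.1 includes it and the Appendix II endpoint list omits it. Under the Appendix II list a small radial hematoma counts while non-actionable femoral bleeding would not.
5. Label the GP IIb/IIIa interaction exploratory. B.1.4 plans a "pre-specified analysis with specific ACT targets in patients receiving GP IIb/IIIa inhibitors to better understand ACT targets and outcomes", and section D modifies the target ranges for these patients, so low, medium and high may not mean the same thing in both strata. The stratum may also be very small.
6. Keep CMH only as an adjusted overall analysis, and correct the label Aim 2 to Aim 4.

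The cost is SAP wording; all three factors are already planned analysis variables. The downside to state is low power: roughly 20–54% if one stratum has no gradient and 7–13% if its gradient is halved, over smaller-stratum shares of 10–50%. A non-significant interaction is therefore not evidence of a uniform effect, and the confidence intervals should carry the interpretation.
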